3.1 Participants

Participants should be recruited from middle school soccer teams. Participants shall fulfill all the following inclusion criteria to be included in the study: (1) be aged between 13 and 18 years; (2) have received at least one year of formal football training; (3) have no history of major sports-related injuries; (4) be in good general health, without smoking or alcohol consumption habits; and (5) have no known psychological or psychiatric disorders that may affect participation; (6) have not participated in any similar intervention within the past year; (7) attend the training sessions regularly. Participants should be excluded according to the following criteria: 1. are outside the age range of 13–18 years; 2. have less than one year of formal football training experience; 3. have a history of major sports-related injuries; 4. have chronic diseases or unhealthy habits such as smoking or alcohol consumption; 5. have known psychological or psychiatric disorders that may affect participation; 6. have participated in similar training interventions within the past year; 7. fail to attend at least 75% of the 12 training sessions.

The required sample size was calculated using G*Power 3.1 software based on a repeated-measures ANOVA (within-between interaction). The average effect size (f) was set at 0.25 (Cherni et al., 2025; Li et al., 2022), with a significance level of 0.05, and the desired statistical power of 0.80 achieved. The calculations indicated that a minimum of 42 participants are required in total, considering the 20% dropout, at least 50 participants should be recruited at the screening session.

The experimental procedures will be explained to participants and their parents at the screening-baseline. Before data collection, the written informed consent should also be provided. During the study, the participants will all attend regular schools and

football trainings. This research should receive approval from the Ethics Committee of University of Macau.

[figure not shown]

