3.2 Study Design and Procedures

This is a randomized controlled trial (RCT) that employs an experimental mixed design where group (traditional Yo-Yo, ball-dribbled Yo-Yo, SSGs) serves as a between-subject factor, while time (pre, post) functions as a within-subject factor. The participants will be randomly assigned to one of the groups: the traditional Yo-Yo group, the ball-dribbled group, SSGs group utilizing computer-based random sorting and grouping, where each participant will receive a number and will then be randomly placed into one of the four groups using Research Randomize ((Karahan, 2012; Shaw et al., 2019) When randomly grouping, the researcher in charge does not participate in the pre- and post-tests.

This research will utilize a non-blinded grouping randomization. The recruited participants who achieve the inclusion criteria will firstly be numbered in sequence then randomly allocated to one of the four groups. Secondly, all participants should experience the baseline testing within 2-weeks before the intervention. The anthropometric parameters, aerobic and anaerobic abilities will be assessed during this stage. The anthropometric indexes and one anaerobic assessment (Wingate Anaerobic Test) will be conducted in kinesiology Laboratory, University of Macau. The aerobic ability and the other anaerobic assessment (Sprint test and Repeated Sprint Ability test) will take place in the playground of a middle school. Then, the intervention will last for four weeks, with 3 training session per week, 12 sessions in total, which will take place in the playground of a middle school. Finally, the post-test stage, all the measurements conducted in the pre-test should be completed within 1-week following the last training session. During the pre- and post-test period, the researchers involved in the test were not informed of the intervention

groups of the subjects. All the procedures are shown in the flow chart as follows (figure 1).

Figure 1 *Study Flowchart*

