3.3 Intervention

Participants will receive traditional Yo-Yo training, ball-dribbled Yo-Yo training, SSGs training respectively. The intervention will last for 4-weeks, with 3 training sessions a week. These interventions will perform as regimens at the same time into the whole training. The first 2-weeks training consists of 2 sets 4-minutes exercise and a 4-minutes passive rest. During the last 2-weeks, the rest between exercise will be reduced to 3-minutes. While training, all the participants should

wear a heart rate belt (Verity Sensebi, Polar, Finland) to monitor the training intensity. Heart rate and RPE will be recorded before, during and after the training.

The Yo-Yo Intermittent Recovery 1 protocol will be implemented as a training tool. Participants should perform 4-minutes repeated 20-meter shuttle runs between two parallel lines, with running pace controlled by standardized audio cues, followed by a 10-second passive rest. The speed will initially start from 10 km/h, increasing by 0.5 km/h every stage. The termination rules will be cancelled, and participants should try to maintain maximum effort regardless of the cues.

The Ball-dribbled Yo-Yo Intermittent training requires participants performing repeated shuttle runs with a soccer ball, simulating dribbling with maximum effort in game. Each shuttle lasts 15 seconds, followed by 15 seconds of passive rest. The required shuttle distance per bout is calculated based on 110% of participant's baseline Yo-Yo IR1 terminal speed. Individualized bout distances will calculate as:

$$D = (V_t \times 110\% / 3.6) \times 15$$
 Where: D = Required shuttle distance per bout (meters), V_t = Terminal speed (km/h) from pre-test Yo-Yo IR1 (Appendix 1) and 3.6 = km/h to m/s conversion. The turning point of the shuttle run will be marked with cone for participant, where participants need to turn 180° with ball dribbled. To ensure continuity of play, two coaches will be positioned near the sidelines to provide replacement balls when necessary.

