3.5 Statistical Analysis

Data analysis will be conducted using SPSS 29.0. First, descriptive statistics will be performed to summarize sample characteristics. Independent samples t-tests will be used to compare baseline differences between groups. The Shapiro-Wilk test will be applied to assess normality; if data violate normality assumptions, appropriate adjustments will be implemented.

A two-way repeated measures ANOVA (group \times time) will be utilized to examine between-group effects, time effects, and interaction effects on outcomes including aerobic and anaerobic performance. If significant interactions are detected, Bonferroni post-hoc tests will be conducted to identify simple main effects.

Effect sizes will be reported as partial eta-squared (η^2) for ANOVA results, with $\eta^2 < 0.06$ considered small, 0.06-0.14 moderate, and >0.14 large. Within-group effect sizes will be calculated using Cohen's d, where $d = 0.2$, 0.5 , and 0.8 represent small, medium, and large effects, respectively. Statistical significance is set at $\alpha = 0.05$, and results will be presented as mean \pm standard deviation (Mean \pm SD).

References

- Akdoğan, E., Yılmaz, İ., Köklü, Y., Alemdaroğlu, U., & Cerrah, A. O. (2021). The effect of isolated or combined small-sided games and speed endurance training on physical performance parameters in young soccer players. *Kinesiology*, 53(1), 78–85. <https://doi.org/10.26582/k.53.1.10>
- Badenhorst, J. (2017). *The effect of the growth spurt on strength, power, speed and agility training in boys during mid-adolescence* [PhD Thesis, North-West University (South Africa), Potchefstroom Campus]. <https://repository.nwu.ac.za/handle/10394/30657>
- Clemente, F. M., Praça, G. M., Aquino, R., Castillo, D., Raya-González, J., Rico-González, M., Afonso, J., Sarmiento, H., Silva, A. F., Silva, R., & Ramirez-Campillo, R. (2023). Effects of pitch size on soccer players' physiological, physical, technical, and tactical responses during small-sided games: A meta-analytical comparison. *Biology of Sport*, 40(1), 111–147. <https://doi.org/10.5114/biolsport.2023.110748>

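### If more than one team is enrolled, randomising within team and adding a team term would gain precision at almost no cost; validity is not at stake

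*Combined protocol and SAP*

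**What the plan says.** Section 3.1 (Participants) gives the source of players: "Participants should be recruited from middle school soccer teams". The same section says "During the study, the participants will all attend regular schools and" football training, so usual training continues for everyone. Section 3.3 (Intervention) places the study exercise inside that training: "These interventions will perform as regimens at the same time into the whole training". The arm-specific part is two 4-minute bouts per session, three sessions a week, for four weeks.

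Section 3.2 (Study Design and Procedures) says that eligible players "will firstly be numbered in sequence then randomly allocated to one of the four groups". It mentions no stratification or blocking by team. Section 3.5 (Statistical Analysis) specifies a two-way repeated-measures ANOVA, group by time, which "will be utilized to examine between-group effects, time effects, and interaction effects on outcomes including aerobic and anaerobic performance". It has no team factor and no covariate.

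The number of teams and their sizes are not stated. Nothing says that the usual team training will be standardised or recorded by team.

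**The concern.** The group-by-time test compares pre-to-post change between arms. A stable difference between teams, such as a higher starting level, cancels in a pre-post difference. Team training that runs during the same four weeks does not cancel, because it acts on the change itself. If teams train differently in that period, part of the spread in change belongs to team, and a model with only group and time leaves that part in the error term. Allocation from one list also lets the arms differ by chance in how many players each team contributes.

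At stake is the precision of the between-arm differences in change that bear on H3 and H4, in a trial planned with 42 players, about 14 per arm.

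**Working it through.** **Inputs from the documents.** Section 3.1: f = 0.25, alpha = 0.05, power 0.80, minimum N = 42, method "calculated using G*Power 3.1 software based on a repeated-measures ANOVA (within-between interaction"). Section 3.2: "group (traditional Yo-Yo, ball-dribbled Yo-Yo, SSGs) serves as a between-subject factor, while time (pre, post) functions as a within-subject factor", so k = 3 arms and m = 2 times. (Section 3.2 also speaks of four groups. Three is used here because three arms are named and three reproduces the stated N; four would give 48.)

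**Assumptions, not in the documents.** Correlation between pre and post rho = 0.5; sphericity correction 1; three teams; share v of the variance in change that is due to team, taken as 0.05, 0.10, 0.20 and 0.30.

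**Step 1: reproduce the planned N.** lambda = f² × N × m / (1 − rho) = 0.0625 × 42 × 2 / 0.5 = 10.5. With F on 2 and 42 − 3 = 39 degrees of freedom, power is 0.803. The stated 42 is reproduced.

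**Step 2: the effect of accounting for team.** Three teams cost two degrees of freedom, giving F(2, 37). The result depends on which variance f = 0.25 refers to, and the plan does not say.

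- *Reading (a), total variance.* The analysis without team has lambda = 10.5. With team balanced across arms and in the model, lambda = 10.5 / (1 − v).
- *Reading (b), within-team variance.* The analysis without team has lambda = 10.5 × (1 − v). With team in the model, lambda stays at 10.5.

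| v | (a) without team | (a) with team | (b) without team | (b) with team | (b) N needed without team |
|---|---|---|---|---|---|
| 0.05 | 0.803 | 0.823 | 0.782 | 0.802 | 45 |
| 0.10 | 0.803 | 0.844 | 0.758 | 0.802 | 48 |
| 0.20 | 0.803 | 0.886 | 0.704 | 0.802 | 54 |
| 0.30 | 0.803 | 0.925 | 0.642 | 0.802 | 60 |

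The last column is rounded up to equal arms. If team explains nothing (v = 0), adding it moves power from 0.803 to 0.802.

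**Step 3: simulation of validity and of the two parts of the fix.** N = 42, 3,000 runs per setting, 2 to 6 teams, team share 0.1 to 0.3, equal arms.

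- Allocation and analysis without team: type I error 0.043 to 0.058, so the nominal 5% is kept.
- Chance imbalance in team-driven change between two arms: SD of 0.09 to 0.11 SD of change at a share of 0.1, and 0.15 to 0.19 at a share of 0.3.
- Stratified allocation without a team term: type I error 0.022 to 0.031 at a share of 0.3. The test becomes conservative, because the allocation removes team imbalance while the error term still carries the team variance.
- Stratified allocation with a team term: type I error 0.042 to 0.059.
- Power with three teams at shares 0.1, 0.2 and 0.3: neither part, 0.821, 0.839 and 0.844; team term alone, 0.828, 0.874 and 0.912; both, 0.844, 0.876 and 0.932.

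The simulated power without team lies above 0.803 because the share is defined there over a population of teams. With only three teams, the expected spread in the sample at a share of 0.3 is about 0.7 + 0.3 × 2/3 = 0.90 of the nominal variance. On that basis the gain at a share of 0.3 is about 9 points (0.932 − 0.844), against 12 points in column (a) of the table (0.925 − 0.803).

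**The case against.** **The premise is not established.** The main support for several teams is a plural noun. Section 3.2 puts the field tests and all 12 sessions in the playground of one middle school, and section 3.3 inserts the interventions into the whole training. This fits one school with shared training, although it does not exclude several teams. A reader might infer that each team has its own coach and load. The documents do not say so. This objection stands, and the point has to be conditional.

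**Validity.** A reader might infer that team differences bias the comparison or could pass for a programme effect more often than the nominal rate. They do not. Players are randomised individually, so chance imbalance by team is already inside the 5% error rate, and the simulation shows this.

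**Power.** A reader might infer that the trial is underpowered because it ignores team. Under reading (a) the plan keeps its 0.80 and a team term only adds to it. A shortfall arises only under reading (b). The 5% to 30% share has no source in the documents, and at 5% the difference is about two points.

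**Stratification itself adds little.** In the simulation with three teams most of the gain at shares of 0.2 and 0.3 comes from the team term; randomising within team adds 0.2 to 2 points on top. This is correct, but it is no reason to leave it out at this cost.

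What remains is that the plan neither rules out several teams nor uses team if there are several, and that using it costs next to nothing.

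**Conclusion.** The point holds as a conditional gain in precision. If more than one team is enrolled and their training differs during the four weeks, the planned analysis leaves team variance in change in the error term. For three teams and an assumed share of 5% to 30%, accounting for team is worth 2 to 12 points of power if f = 0.25 refers to total variance. It recovers 2 to 16 points if f refers to within-team variance. The lower end is negligible and the upper end is material, and the documents do not allow a choice between them. The figures also rest on rho = 0.5, which the plan does not state but which reproduces its N.

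The documents do not support reading this as bias, as an inflated type I error, or as an established loss of the planned power. The change is a cheap improvement, optional rather than essential. With a single team the point falls away.

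**What to change.** State in section 3.1 how many teams will be enrolled. If there is more than one, make both changes below together:

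- **Section 3.2:** list players by team and randomise within each team in permuted blocks of three. Arms are then equal within a team whose size is a multiple of three, and nearly equal otherwise.
- **Section 3.5:** add team as a between-subject factor, so that the model contains team and team × time but no team × group terms. Specify this explicitly. With three teams, main effects only cost two degrees of freedom (39 to 37), whereas a full factorial has nine cells and costs six (39 to 33).

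Stratifying without the team term should be avoided, because it makes the test conservative.

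The cost is one separate randomiser run per team and one degree of freedom per extra team, with no additional players or measurements. The allocation part must be settled before randomisation, since it cannot be repaired afterwards. If only one team is enrolled, nothing needs to change.

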2.1 The Athletic Demands of Soccer Player

Modern soccer demands that players perform frequent high-intensity efforts—such as sprinting, turning, and rapid accelerations—interspersed with periods of lower-intensity activity. These actions vary according to match context and playing position. For instance, midfielders and wide attackers typically perform more high-speed runs than defenders or goalkeepers (Jerome et al., 2024; Sarmento et al., 2024). Although most existing studies focus on adult athletes, similar positional differences are observable in youth soccer players (Gil et al., 2007).

Adolescence is a period of rapid physical development. During puberty, boys experience substantial gains in height, strength, aerobic capacity, and muscular coordination. However, these gains do not occur uniformly and may temporarily disrupt motor control, increasing injury risk (Ribeiro et al., 2024). Therefore, the design of youth training programs must account for both the physiological demands of soccer and the biological variability among athletes.

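### Age, known for every player and spanning 13 to 18, is used neither in allocation nor in the group by time ANOVA; adding it with baseline as a covariate would be a cheap gain in precision

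*Combined protocol and SAP*

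**What the plan says.** - **Eligibility (3.1 Participants).** Players must "be aged between 13 and 18 years". Age has no other role in the design or analysis.
- **Allocation (3.2 Study Design and Procedures).** Players are numbered and assigned "utilizing computer-based random sorting and grouping". No stratification, blocking or minimisation is described.
- **Analysis (3.5 Statistical Analysis).** The model is an ANOVA with group, time and their interaction, and no covariate. Baseline differences are examined by t-tests, but nothing in the model follows from them.
- **Sample size (3.1).** The calculation is "based on a repeated-measures ANOVA (within-between interaction"), with these settings: "The average effect size (f) was set at 0.25", "with a significance level of 0.05, and the desired statistical power of 0.80 achieved". The result is "a minimum of 42 participants are required in total, considering the 20% dropout, at least 50 participants should be recruited".
- **Background (2.1 The Athletic Demands of Soccer Player).** Gains in puberty are described as large and uneven, and youth training programmes, in their design, "must account for both the physiological demands of soccer and the biological variability among athletes".

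**The concern.** Section 1.1 presents puberty as a time of marked gains in strength, speed, endurance and skill under training, and 2.1 adds that growth is uneven. A 13-year-old and an 18-year-old may therefore differ both in level of performance and in response to four weeks of training. With 14 to 17 players per arm, simple random allocation can leave the arms visibly different in mean age.

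If age predicts the outcome beyond what the model already removes, leaving it out inflates the residual variance of the between-arm test and may blur the comparison. H3 and H4 turn on contrasts between pairs of arms, and planned power is only 0.80. If one arm happens to be clearly older, readers will ask whether age explains the result. The plan has no prespecified adjustment with which to answer, and one chosen after seeing the data would be less credible.

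**Working it through.** **1. Reproduce the stated sample size.** Inputs from 3.1 and 3.2: f = 0.25, alpha = 0.05, power 0.80, k = 3 arms, m = 2 time points. Section 3.2 also speaks of four groups but names three, so three is used. The pre-post correlation rho is not given; 0.5 is assumed.

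- Noncentrality: lambda = f² × N × m / (1 − rho) = 0.0625 × 42 × 2 / 0.5 = 10.5.
- Degrees of freedom: (k − 1)(m − 1) = 2 and (N − k)(m − 1) = 39.
- Power = 0.803, and 42 is the smallest N that reaches 0.80. The stated figure reproduces.

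**2. Chance imbalance in age.** The age distribution is not given. Ages uniform over 13-18 are assumed, so SD = 5/√12 = 1.44 years. The arms hold 42/3 = 14 or 50/3 ≈ 17 players. The SE of a two-arm difference in mean age is SD × √(2/n): 0.55 year at 14 per arm and 0.50 at 17. The chance of a gap above 0.75 year is below. The given-pair column is the normal tail beyond 0.75/SE; the largest-gap column comes from 40,000 simulated allocations.

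| Assumption | Given pair | Largest gap among three arms |
|---|---|---|
| Uniform, 14 per arm | 17% | 36% |
| Uniform, 17 per arm | 13% | 28% |
| SD 1.2, 17 per arm | 7% | 16% |
| SD 1.0, 14 per arm | 5% | 12% |

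**3. Is the planned test biased?** No. In 6,000 simulated trials per scenario with no group effect, the rejection rate of the change-score test was 4.7% to 5.2%, whether age was unrelated to the outcome, related to level only, or related to the change as well.

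**4. Age related to level only, planned analysis.** With two time points, the interaction is a comparison of mean pre-post change, so a constant age effect subtracts out. Simulated power was 0.80 without age and 0.79 with it.

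**5. Age related to the four-week change.** Let R² be the share of change-score variance that age explains. The documents give no figure, so a range is shown. Adding age gives lambda = 10.5 / (1 − R²), with 39 − 1 = 38 denominator degrees of freedom.

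| R² | lambda | Power with age |
|---|---|---|
| 0 | 10.5 | 0.803 |
| 0.05 | 11.1 | 0.824 |
| 0.10 | 11.7 | 0.845 |
| 0.20 | 13.1 | 0.886 |
| 0.30 | 15.0 | 0.925 |

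Without age, power is 0.803. Simulation agrees: 0.84, 0.88 and 0.92 at R² = 0.10, 0.20 and 0.30, against 0.80-0.81 without age.

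**6. Baseline-adjusted model (post on group and baseline), age related to level only.** At rho = 0.5, baseline alone cuts the residual variance from 1 (change score, in units of the outcome variance) to 1 − 0.5² = 0.75, so lambda = 10.5/0.75 = 14. Simulated power is 0.90. Suppose age explains half of the stable between-player variance, that is 0.5 × 0.5 = 0.25 of the outcome variance. Given age, the variance is 0.75 and the pre-post covariance 0.25, so the residual variance after both covariates is 0.75 − 0.25²/0.75 = 0.667 and lambda = 10.5/0.667 = 15.75. Simulated power is 0.93. If age explains none of the level, adding it moves simulated power from 0.90 to 0.89.

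**The case against.** The strongest reply is that an unstratified, unadjusted randomised comparison is valid. Chance imbalance is part of the sampling error that the F test already allows for, and a stable age effect on level cancels in the planned interaction. All of that stands (steps 3 and 4). The gain over the planned test then depends on how far age predicts the change, which the documents do not quantify. Much of the improvement under ANCOVA comes from the baseline value rather than from age: about 0.80 to 0.90 from baseline, then 0.90 to 0.93 from age in the step 6 scenario. Chronological age is also only a rough stand-in for maturity.

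Two stronger readings are tempting, and the documents support neither.

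- **That the trial breaks its own rule.** A reader might infer this from the statement in 2.1 that "must account for both the physiological demands of soccer and the biological variability among athletes". The subject of that sentence is the design of youth training programmes, in a literature review. It sets no requirement for allocation or analysis.
- **That omitting age will distort or bias the comparison.** Type I error stays near 5%. The most that can be said is that imbalance may blur the comparison if age predicts what the model leaves unexplained.

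The objection does not remove the case for the covariate. Age and baseline values are already collected, the possible gain is material for a trial planned at 0.80 power, and the largest loss seen in simulation was about 0.01.

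**Conclusion.** The point holds as an inexpensive improvement in precision and interpretability, not as a flaw that invalidates the planned test. With 14 to 17 players per arm and ages spread evenly over 13-18, a gap of more than 0.75 year somewhere among the three arms would be common, though clearly less so for any one pair or under a narrower age spread. The 0.75-year threshold is illustrative and is not tied to a known effect on any outcome.

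The power gain from age ranges from nothing, if age is unrelated to what the model leaves unexplained, to about 0.12 in the change analysis if age explains 30% of the change (0.925 − 0.803). These figures rest on an assumed pre-post correlation of 0.5, which is the value that reproduces the plan's 42, and on assumed strengths of the age relation.

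**What to change.** In 3.5, prespecify the between-arm comparison for each performance outcome as an ANCOVA of the post-test value on group, the baseline value of that outcome and age at baseline (continuous), with the planned Bonferroni-adjusted pairwise contrasts taken from this model. State that the covariates are fixed in advance and do not depend on the baseline t-tests.

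The cost is one degree of freedom for age (and one for the baseline value) and a sentence of SAP text. No new data are needed.

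Optionally, generate the allocation list in blocks within two age bands, for example 13-15 and 16-18. This means two short lists instead of one. It is not needed for the covariate change to be worthwhile, and maturity differences within a band would remain.

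### Exclusion criterion 7 (fewer than 9 of the 12 intervention sessions) can be applied only after randomisation, and no all-randomised analysis is defined, so the between-arm comparisons can be biased

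*Combined protocol and SAP*

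**What the plan says.** Section 3.1 (Participants) gives seven inclusion and seven exclusion criteria. The last exclusion criterion applies to players who "fail to attend at least 75% of the 12 training sessions". The last inclusion criterion asks that they "attend the training sessions regularly", with no number and no period.

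Section 3.2 (Study Design and Procedures) identifies the sessions: the intervention runs for four weeks, "with 3 training session per week, 12 sessions in total". It also gives the order of events. "The recruited participants who achieve the inclusion criteria will firstly be numbered in sequence then randomly allocated to one of the four groups". Then: "Secondly, all participants should experience the baseline testing within 2-weeks before the intervention". Training follows, and post-tests fall within one week of the last session. Allocation is open to players: "This research will utilize a non-blinded grouping randomization". (The count of four groups conflicts with the three arms named elsewhere in the section. That is a separate matter.)

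Section 3.5 (Statistical Analysis) plans a group by time repeated-measures ANOVA. It names no analysis set, whether all-randomised or per-protocol, and gives no rule for a missing post-test and no sensitivity analysis.

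**The concern.** An eligibility criterion should be settled before allocation. This one depends on what a player does under the assigned arm, so applying it makes membership of the analysed groups partly a consequence of the arm. Randomisation protects the comparison of the groups it formed. It does not protect a comparison of those who went on to attend.

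H3 and H4 in section 1.4 are between-arm claims: equivalence for one pair of arms and superiority over the third. If low attenders would have improved less, an arm that loses more of them will look better than it is. The post-test window is one week, so low attenders who are not invited leave a gap that no later analysis can fill.

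**Working it through.** **When the criterion can be known.** 75% of 12 sessions is 0.75 × 12 = 9, so a player with 8 or fewer meets the exclusion criterion. The order in section 3.2 is eligibility, allocation, baseline tests, 12 sessions, post-tests. With four sessions missed (12 − 8 = 4) a player fails the rule, and this cannot happen before the fourth missed session. The criterion is therefore always applied after allocation.

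**Whether anything restores the excluded players.** Section 3.5 does not mention them. A repeated-measures ANOVA with two time points needs both measurements, so a player without a post-test drops out of it in any case.

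**How large the bias could be.** The documents give no attendance rates and no correlation of attendance with change, so every input here is assumed. Suppose the lowest fraction q of an arm is removed on a standard normal attendance score that has correlation r with change. The mean change of those who remain shifts by

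shift = r × φ(z_q) / (1 − q).

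- q = 0.2: φ(−0.842) / 0.8 = 0.280 / 0.8 = 0.350. The shift is 0.105 SD at r = 0.3 and 0.175 SD at r = 0.5.
- q = 0.3: φ(−0.524) / 0.7 = 0.348 / 0.7 = 0.497. The shift is 0.149 SD at r = 0.3 and 0.248 SD at r = 0.5.

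The bias in a two-arm difference is the difference between the two arms' shifts:

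| Removed, arm A / arm B | r in A / r in B | Bias (A − B) |
|---|---|---|
| 20% / 20% | equal | 0 |
| 20% / 20% | 0.5 / 0.3 | 0.175 − 0.105 = 0.070 SD |
| 20% / 0% | 0.3 in A | 0.105 SD |
| 20% / 0% | 0.5 in A | 0.175 SD |
| 30% / 0% | 0.3 to 0.5 in A | 0.149 to 0.248 SD |

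The second row shows that equal removal rates are not enough if players miss sessions for different reasons in different arms.

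**Simulation check.** Assumed: 17 per arm, no true difference, 4,000 trials per scenario, one-way comparison of the outcome across arms.

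- 20% removed from every arm: the spurious difference between the third and first arms lay between −0.005 and 0.014 SD, and type I error between 4.7% and 5.4%.
- 10%, 10% and 40% removed: the spurious difference was 0.14 SD at r = 0.3 and 0.23 SD at r = 0.5. Type I error was 5.7% and 8.2%, against 4.3% and 5.5% in the same trials when all randomised players were kept.

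**Against the noise.** With 14 to 17 players per arm, the standard error of a two-arm difference is √(2/17) = 0.34 to √(2/14) = 0.38 SD. A shift of 0.105 to 0.175 SD is thus 0.105/0.38 = 0.28 to 0.175/0.34 = 0.51 of one standard error.

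**The case against.** Much can be said in the plan's favour, and several stronger statements that a reader might infer are not supported.

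- **That the plan commits itself to deleting the data and reporting a per-protocol result as the trial result.** Section 3.1 says such players should be excluded. It does not say that their post-tests are skipped or their data dropped, and the flowchart is not available in the text reviewed. Removal is the natural reading when no analysis set is defined, but it remains a reading.
- **That inclusion criterion 7 has the same defect.** It may mean usual football training, which can be checked at screening. The point rests on exclusion criterion 7 alone.
- **That attendance is known to depend on the arm.** It is only plausible. Section 1.1 suggests that small-sided games may be more enjoyable, and allocation is open. But section 3.3 asks for maximal effort in all three arms and sets the regimens within the players' overall training, so absence may owe much to school or team factors common to all arms.
- **That up to 10 of 50 players could be lost to this rule.** That figure is only the planning allowance for dropout in section 3.1 (20% of 50). It is neither a forecast nor a ceiling for low attendance, and the plan does not say whether low attenders are counted in it.

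It is also fair to say that the illustrated bias is well under one standard error, and that for equivalence claims an all-randomised analysis can dilute a real difference, so the adherent subset carries weight of its own. Both points stand. Neither justifies collecting and analysing adherent players only. The standard error can be stated in advance, whereas the bias cannot be bounded once the low attenders' outcomes are missing. Reporting both sets answers the equivalence point.

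**Conclusion.** The concern holds for exclusion criterion 7. Followed as written, the plan removes randomised players according to their compliance with an openly allocated arm, and it defines no all-randomised analysis. The right description is that this can bias the comparisons behind H3 and H4. It does so if attendance differs by arm, or for different reasons by arm, and is related to outcome.

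The documents do not allow the size to be estimated. It runs from about 0, when removal is equal and of the same kind across arms, to about 0.11 to 0.18 SD when 20% of one arm and none of another is removed at assumed correlations of 0.3 to 0.5. The upward direction rests on the further assumption that low attenders improve less. The change should be made before enrolment, because outcomes not collected in the post-test week cannot be recovered.

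**What to change.** 1. Delete exclusion criterion 7 as an eligibility rule. State that inclusion criterion 7 means usual football training before enrolment, or delete it if it means the intervention sessions.
2. Invite every randomised player to the post-test, whatever their attendance.
3. In section 3.5, define the main analysis as all randomised players in the arm assigned, using a method that keeps players with a missing post-test, for example a mixed model for group by time. State its missing-data assumption. The model supplements post-testing low attenders and does not replace it.
4. Report attendance by arm. Report the subset with at least 9 of 12 sessions as a labelled per-protocol analysis beside the main one, in particular for the equivalence parts of H3 and H4.

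The cost is protocol wording and the post-testing of a few low attenders. Sprint, repeated-sprint and aerobic tests are at a middle school playground, but anthropometry and the Wingate test need a visit to the university laboratory. Some absentees, such as injured players, may be unable to do maximal tests, which is why the missing-data method is needed. The estimated effect may be slightly smaller than among compliers.
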